EAGLE is an international quality improvement programme to share best practice and harmonise procedures for surgeons and the theatre teams so that they might perform the best possible anastomosis for each particular patient. This programme has 3 main approaches: (i) preoperative risk stratification (making sure for each patient that it is safe to join the bowel together); (ii) harmonisation of surgical technique (making the join as good as it can be and checking it carefully after it is created), and (iii) implementation of an intra-operative, anastomosis 'checklist' (focusing the attention of the whole theatre team at this critical stage of the operation). We will use a novel scientific approach to assess the patient benefit that enables not only the quality improvement itself to be delivered to all participating hospitals but also enables collection and analysis of data to measure the effect of these measures. The best way of doing this is to embed our proposed quality improvement into a staggered implementation programme, allowing the effect to be assessed between the centres. The specific methodology proposed introduces the intervention in

a stepwise fashion to all hospitals. By the end, all sites will have implemented the programme. Overall, we hope to reduce the leak rate by 30% from 8.1% to 5.6% in about 4,500 patients.

The European Society of Coloproctology (ESCP) with Birmingham Surgical Trials Consortium and Queen Mary University of London Pragmatic Clinical Trials Unit have developed an international network of hospitals and surgeons to deliver the EAGLE study; a 2015 audit included approximately 1,000 surgeons in 284 hospitals from 39 countries and our network has grown now to about 50 countries. The impact of this study can be ground-breaking not only from the perspective of patient safety and thence quality of life, but also because the methodology proposed could be used to improve and standardise surgical quality for many other operations and processes around surgery in the future, in countries with both well developed and less developed surgical services.

BACKGROUND

Clinical problem

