 To determine the effect of QII on anastomotic leak rate in pre-defined subgroups of clusters or patients.

Secondary process objectives

- To assess the feasibility of a new study design / methodology for evaluating complex interventions such as surgery. This will be assessed by measuring the total number of participating hospital and countries, attrition rate during study set-up, time taken for study set-up at sites, overall time to complete recruitment of sites and patients to the study.
- To evaluate change in behaviour around anastomotic practice following implementation
 of the Safe-anastomosis intervention by monitoring the proportions of patients undergoing
 anastomosis, anastomosis with defunctioning stoma, and defunctioning stoma during the
 study period.
- To assess adherence to completion of the online Safe-anastomosis educational module and implementation of the Safe-anastomosis checklist within surgical teams.

STUDY DESIGN

Study Design

EAGLE is an international, multicentre, cluster-sequence randomised controlled study evaluating the impact of implementation of the *ESCP Safe-anastomosis Intervention* on anastomotic leak rates following right colectomy.

The intervention will be delivered at hospital-level so randomisation will be by hospital, with outcomes assessed at the individual patient level. To ensure that the study is attractive for potential collaborators to participate, all hospitals will implement the quality improvement programme, including those randomised to only collect pre-intervention data. To prevent baseline data gradually becoming contaminated by prior knowledge of the intervention or other unrelated background changes in patient care, we aim to complete data collection within 12 months.

[figure not shown]

Figure 1: Dog-leg design

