 - All patients undergoing right colectomy are eligible, including those who do not have an anastomosis and are defunctioned by a proximal stoma.
- Procedures for any pathology, via any operative approach (open, laparoscopic, robotic or converted) are eligible.
- Elective (surgery on a planned admission), expedited, and emergency (surgery on an unplanned admission) procedures are eligible.

Patient exclusion criteria

- Patients undergoing more than one gastrointestinal anastomosis during the same operation.
- In Crohn's disease, additional upstream strictureoplasty or resection/anastomosis to treat disease or strictures at the same operation.
- Simultaneous right colectomy and hyperthermic intraperitoneal chemotherapy (HIPEC) and/or cytoreductive surgery.
- Each individual patient should only be included in EAGLE once. Following the index procedure that is included in EAGLE, patients undergoing additional procedures within the study window should not be included for a second time.

Selection bias

Selection bias will be closely monitored by the Study Management Group. EAGLE coordinators will regularly liaise with site Principal Investigators to ensure that all eligible patients are entered into the EAGLE study. Recruitment rates will be monitored across individual sites and clarification will be sought in case of a drop in recruitment that might indicate that eligible patients were not included. An independent validation process will monitor case ascertainment (see *Monitoring* and *Data Validation*, page 24-25).

PATIENT IDENTIFICATION

Each participating country and hospital will decide how best to identify eligible patients.

Patients can be identified either before, during, or after surgery. As guidance, it is anticipated that patients may be identified from any of the following settings, but that this should preferentially be performed pre-operatively:

- Pre-operatively: surgical outpatient clinics (e.g. when the patient is being booked for elective surgery); planned theatre lists (e.g. at the time of admission for surgery); emergency surgical admissions (e.g. at the time that a decision to operate is made)
- Intra-operatively: by the operating surgical teams during the in-theatre Safe-anastomosis checklist, once the procedure eligibility has been confirmed.
- Post-operatively but before discharge: by either the operating surgeon or by review from the research team.

Patients will be identified by a suitable person who may include:

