The study intervention will be introduced at a specific timepoint determined by the randomisation sequence. Sites will not be exposed to the study intervention before their allocated timing and this will be ensured by time-locked password access to QII materials.

Intervention details

The EAGLE Safe-anastomosis Quality Improvement Intervention (QII) is a behavioural change intervention composed of three parts:

1. Routine patient-level stratification of risk of anastomotic leak

Calculation of a preoperative risk for each patient undergoing right colectomy or ileocaecal resection using the anastomoticleak.com risk calculator. This includes six factors: Gender; Body Mass Index >30; Anticoagulant use; Intraoperative complication; Serum protein level; Hospital size. Investigators will be trained and encouraged to preoperatively calculate the risk with or without an intraoperative complication. This risk estimate will be used to inform shared decision

making with the patient preoperatively, and will be reviewed in light of intraoperative events as part of the ECSP Safe-anastomosis Checklist.

2. ESCP Safe-anastomosis Checklist

The ESCP Safe-anastomosis Checklist will be implemented in-theatre, immediately prior to the time of formation of an anastomosis or formation of a stoma; this can be before or after transection of the bowel. The checklist should be completed by an unscrubbed member of the theatre team in partnership with the operating surgeon(s), other members of the surgical team, the scrub nurse(s), anaesthetist(s) and operating department practitioner(s).

The Safe-anastomosis checklist (Appendix 1) consists of:

- (1) Review of any concerns from the anaesthetist, including the anaesthetic risk, haemodynamic instability, vasopressors, blood transfusion, operating time greater than 4 hours, or blood loss greater than 100mls;
- (2) Review of any concerns from the surgical team, including the surgeon, scrub staff and operating theatre practitioners. A consensus decision for primary anastomosis (with or without defunctioning enterostomy) or defunctioning enterostomy without anastomosis will be then made by the operating surgeon.
- (3) If the consensus decision is to proceed with anastomosis; planning equipment, anastomotic configuration, and delivery of an agreed anastomotic technique, including intra-operative checking of anastomosis integrity.

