The primary outcome measure is anastomotic leak within 30-days of surgery (with Day 0 as the day of surgery). The denominator for the primary outcome is the total for patients who had a primary anastomosis. The numerator is anastomotic leak, defined as a composite of either:

Anastomotic leakage identified radiologically or clinically

or

Intraperitoneal (abdominal or pelvic) fluid collection identified radiologically, as per the
 Centre for Disease Control Criteria for Organ Space infection

SECONDARY OUTCOME MEASURES

The denominator is the total for patients who had a primary anastomosis:

Reoperation for anastomotic leak, within 30-days

The denominator is the total for all patients:

- Reoperation for any cause, within 30-days
- Unplanned admission to critical care, within 30 days
- Readmission within 30 days.
- · Length of hospital stay, up to 30-days
- Mortality within 30-days.
- Rate of ileostomy without anastomosis.
- Rate of defunctioning ileostomy with anastomosis.

PROCESS EVALUATION

Adherence to the key components of the intervention will be recorded on the Anastomosis Checklist. This will be a printed sheet which is completed by a circulating staff member in theatre. Specifically they will record:

- Whether pre-operative risk stratification was performed.
- Whether intra-operative risk stratification was performed.
- Whether the surgeon participated in the Anastomosis Checklist.

This process will be co-ordinated by the Theatre Nurse co-Principal Investigator. At the end of the operation, the Anastomosis Checklist will be filed in the patient notes. This will subsequently be accessed by the data collection team to extract data to the CRF.

DATA COLLECTION AND FOLLOW-UP

Data will be collected in two phases. During the index admission pre-operative and intra-operative data will be collected. Local Principal Investigators will establish pathways in their hospitals to ensure robust data collection; for example, pre-operative data could be collected on the morning prior to surgery, with intra-operative data fields completed in theatre immediately following completion of the procedure. Alternatively all data could be collected in theatre, or in the post-operative ward.

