STATISTICAL ANALYSIS PLAN

This will be conducted on an intention-to-treat basis i.e. all patients recorded in the database during the scheduled 2-month recruitment periods will be included, and those in the second period will be considered exposed to the intervention regardless of whether learning from the intervention was actually implemented. The primary outcome will be 30-day anastomotic leak rate. In the primary analysis, 30-day leak rate will be modelled using mixed effects logistic regression with random cluster (hospital) effects allowing inclusion of baseline risk factors such as co-morbid disease and ASA score and adjustment for a fixed time effect between time periods.

Planned additional analyses

Pre-planned exploratory sub-group analyses of the primary outcome will be performed in the following groups:

At cluster (hospital) level:

- Number of beds (<500 versus ≥500 total hospital beds).
- Right colectomy volume (<10 patients versus ≥10 patients per 2 month period).
- Early adoption (early versus late study entrants).
- Health service expenditure per capita in purchasing parity (top versus middle versus bottom tertile).
- Proportion of operating surgeons in each centre completing the online training modules prior to 'post-implementation' data collection (high [≥80%], intermediate [50-79%], low [<50%]).
- World Bank income group (high versus middle/low income country).

At patient level:

- Indication for surgery (malignant versus benign, e.g. inflammatory bowel disease).
- Procedure urgency (elective versus expedited/ emergency).
- Age (≤65 years versus >65 years).
- Operative approach (open versus laparoscopic/ robotic).
- Anastomotic technique (stapled versus handsewn anastomosis).
- Primary operating surgeon experience as reported (trainee versus consultant).
- Primary operating surgeon specialism as reported (general versus colorectal surgeon).

Reverse analysis will also be undertaken to explore what are the characteristics of hospitals with a big change versus no change, and do these differ in respect of cluster characteristics.

DATA HANDLING AND RECORD KEEPING

Source Data

Source data within the EAGLE study will be kept as part of the participants' medical notes generated and maintained at site. As all data collected and analysed within the EAGLE study are routinely collected, source data will only be within the medical notes.

Data Management

Information will be collected at the following times:

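### The primary leak rate counts only patients who received an anastomosis, a decision the intervention targets, so part of any fall may reflect selection rather than safer anastomoses

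*Protocol*

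**What the plan says.** The Protocol enrols every right colectomy. Under Patient inclusion criteria: "All patients undergoing right colectomy are eligible, including those who do not have an anastomosis and are defunctioned by a proximal stoma". The primary outcome is narrower: "The denominator for the primary outcome is the total for patients who had a primary anastomosis" (Primary outcome measure). Its numerator is a clinical or radiological leak, or a radiologically identified abdominal or pelvic collection.

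The intervention acts on who enters that denominator. The Plain English Summary describes its first approach as "making sure for each patient that it is safe to join the bowel together". Under Intervention details, the checklist leads to a choice: "A consensus decision for primary anastomosis (with or without defunctioning enterostomy) or defunctioning enterostomy without anastomosis will be then made by the operating surgeon". The Secondary process objectives plan to evaluate changed practice after the introduction "of the Safe-anastomosis intervention by monitoring the proportions of patients undergoing" anastomosis or stoma.

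The Statistical Analysis Plan section of the Protocol describes the analysis as intention-to-treat and says that "all patients recorded in the database during the scheduled 2-month recruitment periods will be included". The primary model is a mixed-effects logistic regression "allowing inclusion of baseline risk factors such as co-morbid disease and ASA score". Among the secondary outcomes with all patients as denominator is "Rate of ileostomy without anastomosis".

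**The concern.** Membership of the primary denominator is fixed after allocation, by surgeons who know the allocation (Blinding), through a decision that the programme is meant to inform. If the programme leads some high-risk patients to a stoma without anastomosis, they leave both numerator and denominator under exposure but stay in both under control. The anastomosed patients in the two conditions are then no longer the groups that randomisation made comparable. The leak rate can fall although the leak risk of an anastomosis is unchanged in every patient.

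What is at stake is the reading of the primary result. The stated aim concerns leak after right colectomy, while the outcome concerns leak after an anastomosis was chosen. A fall could come from better technique, from different patient selection, or from both, and the primary estimate cannot tell these apart and gives no weight to additional stomas. Baseline covariates such as ASA score help only in part, because the checklist also reviews intraoperative findings.

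**Working it through.** **1. The plan's own figures.** Inputs from the Sample Size section: 8.1% and 5.6%, 80% power, 5% significance (taken as two-sided), ICC 0.05 without decay, 10 patients per hospital per period.

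- Individually randomised: n per arm = [1.960·√(2 × 0.0685 × 0.9315) + 0.842·√(0.081 × 0.919 + 0.056 × 0.944)]² / 0.025² = 1,602, or 3,204 in total.
- Dog-leg design effect, in units of the patient-level variance: a hospital-period mean has variance 0.05 + 0.95/10 = 0.145. Each of the two within-period contrasts has variance 0.29, and their covariance is −0.05 through the middle sequence. Their average has variance (0.29 + 0.29 − 0.10)/4 = 0.12 per triplet. For 40 individually randomised patients it would be 2/20 = 0.10. The design effect is 1.20.
- 3,204 × 1.20 = 3,845 patients, and × 3/40 = 288 clusters. With the 14% inflation: 4,383 and 329. The Protocol states 3,895 and 292, then 4,440 and 333. Agreement is within about 1.3%.

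The target of 2.5 points at 80% power implies a standard error of 2.5/(1.960 + 0.842) = 0.89 points.

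**2. Selection alone.** Assumptions not in the Protocol: 5% have no anastomosis under control, and diverted patients have a leak risk of 25%. No patient's own risk changes.

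- Control: 95% × 8.1% = 7.695 leaks per 100 patients.
- Divert 3 more per 100: (7.695 − 0.75)/92 = 6.945/92 = 7.55%. The fall is 0.55 points, and 0.55/2.5 = 22% of the target.
- Divert 5 more per 100: (7.695 − 1.25)/90 = 6.445/90 = 7.16%. The fall is 0.94 points, and 0.94/2.5 = 38% of the target.

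The approximate chance of a significant result in favour is 1 − Φ(1.960 − fall/0.89), about 9% and 18%, against 2.5% with no effect.

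**3. Range.** Let q be the share of otherwise anastomosed patients who are diverted and r their mean leak risk. The primary rate becomes (8.1% − q·r)/(1 − q).

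| q | r | Primary rate | Share of 2.5 points | Chance of significance |
|---|---|---|---|---|
| 2% | 25% | 7.76% | 14% | 6% |
| 5% | 20% | 7.47% | 25% | 10% |
| 5% | 30% | 6.95% | 46% | 25% |
| 10% | 20% | 6.78% | 53% | 32% |
| 10% | 25% | 6.22% | 75% | 56% |

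Reaching 5.6% by selection alone needs q = 2.5/(r − 5.6), with r in percentage points: 17.4% at r = 20, 12.9% at 25, 7.3% at 40.

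**4. All-patient measures in the 3-per-100 case.**

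- Counting every patient without an anastomosis as event-free: 7.695% to 6.945%, a fall of 0.75 points. That is larger than the 0.55 points in the primary outcome.
- Counting collections as recorded: if patients without an anastomosis have a collection risk c, the fall is 3 × (0.25 − c) points. It is 0.75 at c = 0 and 0.45 at an assumed c = 10%.
- Leak, collection or no anastomosis: 5 + 7.695 = 12.7% to 8 + 6.945 = 14.9%. Each diverted patient adds 1 and removes r, so this measure rises by 3 × (1 − 0.25) = 2.25 points by construction.

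No single measure settles the matter. They have to be read together.

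**The case against.** Selection is part of the programme. The Protocol's background names it as a risk factor for leak, and avoiding an anastomosis in a high-risk patient is an intended effect. A reader might infer that a significant reduction would mean nothing more than relocated patients. The documents do not support that: a fall by this route is a programme effect, though not evidence that anastomoses became safer.

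Much of the needed information is already planned. Patients without an anastomosis are followed to day 30. Mortality, any reoperation, unplanned critical care, readmission, length of stay and both ileostomy rates use all patients. A shift would be visible. This stands, but it leaves the primary estimate as it is.

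Diversion is also not established. Clinicians keep their judgement (Ethics & Consent). A high-risk patient may receive a defunctioning stoma with an anastomosis and so remain in the denominator. Diversion of 1 to 2% would explain little.

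A reader might also see a flat contradiction between the intention-to-treat sentence and the restricted denominator. It is mostly wording. The sentence goes on to define exposure regardless of actual implementation, and the outcome sections set a denominator for each outcome, so the two can be read together.

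Finally, a separate statistical analysis plan, not seen here, may contain an all-patient analysis. That would meet much of the fix. The denominator itself is fixed in the Protocol.

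**Conclusion.** The concern holds as a limit on interpretation. The primary denominator depends on a post-allocation decision that the intervention targets, so part of a fall in the leak rate may reflect who was anastomosed. Under the stated assumptions (5% without anastomosis at baseline, 3 to 5 more per 100 diverted, 25% risk) that part is 0.55 to 0.94 points, or 22 to 38% of the target. Over the wider range shown it runs from 14% to 75%. The Protocol supplies none of these inputs, and the whole target would need roughly 7 to 17% diversion of patients at 20 to 40% risk.

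It does not follow that a lower rate would be wholly spurious. Nor does it follow that the claim of benefit should hinge on the composite of leak, collection or no anastomosis. That composite treats a stoma as equal to a leak and rises with any diversion, however appropriate, so its worsening is not in itself evidence of harm.

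**What to change.** Keep the primary outcome as defined. Pre-specify, before the data are unblinded, the same mixed model in all eligible right colectomy patients for:

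1. leak or intra-abdominal/pelvic collection as recorded for every patient, with or without an anastomosis (not coded as absent where there is none);
2. the composite of leak, collection or no anastomosis.

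Report both beside the primary result, together with the rate of ileostomy without anastomosis. Set no rule that makes the claim of benefit depend on the second analysis. State in advance that a lower primary rate accompanied by more stomas is not by itself evidence of safer anastomoses.

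Reword the intention-to-treat sentence so that including all recorded patients refers to classification by allocated exposure and to the all-patient analyses, with the primary outcome restricted to patients with a primary anastomosis.

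The cost is some wording and two further model fits. No new data are needed: all patients are followed up (Data Collection and Follow-up), and the case report form in Appendix 2 records the absence of an anastomosis and does not make its leak/collection item conditional on one. The small downside is that a positive primary result may be tempered by the all-patient analyses.

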All patients, including those who did not have a primary anastomosis, will be followed-up to a maximum of 30-days postoperatively (with Day 0 being the day of surgery) by a review of their inpatient health records, routine clinic visit letters, and reports for postoperative radiological investigations arranged as part of normal patient care. There will be no additional patient contact (telephone or in-person) beyond what is normal clinical practice at each centre. The study is designed efficiently so that existing patient follow-up pathways and health records can be used, with only data that is routinely collected as part of normal clinical care being captured.

Most anastomotic leaks following ileocolic anastomosis occur in the early post-operative period (days 4-14). Although a small number of anastomotic leaks occur beyond day 30, limiting follow-up to 30 days will ensure that the vast majority of leaks are captured.

SAMPLE SIZE

Assuming no decay in the intracluster correlation over time, our 2015 data suggest an ICC of approximately 0.05 [REF 2017]. Based on feasibility (below), we assume that each hospital provides data on 10 patients over a 2-month recruitment period (5 per hospital per month). An overall 'design effect' or sample size inflation factor for our cluster-randomised dogleg design relative to an individually randomised parallel groups design can then be calculated. Using this design effect, to detect a 30% relative risk reduction in leak rate from 8.1 to 5.6% with 80% power at the 5% significance level requires 292 clusters and 3,895 patients. In practice there will be variation in recruitment at different hospitals, which can be expected to increase the required sample size. Following a published rule of thumb, we assume that this inflates the sample size by at most 14% leading to a required sample size of 333 clusters and 4,440 patients.

PROJECTED RECRUITMENT

Data for 3,208 right colectomies was submitted by 284 centres over a 2 month period to the 2015 ESCP Right Hemicolectomy Audit; an average of 11.3 patients per 2 months. 81% the sites recruited >10 patients over the 2-month period. A mean of 10 patients per centre is required for each 2 month recruitment period.

Patients per centre (2 months)	Proportion of centres
1-5	19% (n=53)
6-10	37% (n=104)

11-15	22% (n=63)
16-20	14% (n=39)
21-30	6% (n=17)
31+	3% (n=8)

Table 1: Patient recruitment data from 2015 ESCP Right Colectomy & Ileocaecal Resection Audit

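### The protocol says 81% of audit sites exceeded 10 patients where its own table gives 45%, and its sample size makes no stated allowance for eligible patients who have no anastomosis

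*Protocol*

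**What the plan says.** The protocol's Sample Size section takes its recruitment rate from feasibility data: "Based on feasibility (below), we assume that each hospital provides data on 10 patients over a 2-month recruitment period". Under Projected Recruitment it reports the 2015 audit, with 3,208 right colectomies from 284 centres, or "an average of 11.3 patients per 2 months". It then says "81% the sites recruited >10 patients over the 2-month period", and adds: "A mean of 10 patients per centre is required for each 2 month recruitment period". Table 1 gives the distribution of centres by number of patients.

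The calculation assumes that "our 2015 data suggest an ICC of approximately 0.05" and is set "to detect a 30% relative risk reduction in leak rate from 8.1 to 5.6% with 80% power". It arrives at 292 clusters and 3,895 patients. An allowance of at most 14% for unequal recruitment raises these to 333 and 4,440. The protocol summary gives the 4,440 as participants.

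On who is counted, the patient inclusion criteria say: "All patients undergoing right colectomy are eligible, including those who do not have an anastomosis". The primary outcome section says: "The denominator for the primary outcome is the total for patients who had a primary anastomosis".

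**The concern.** There are three separate matters.

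- **The 81% figure.** It stands directly above a table that contradicts it, in the text offered as support for 10 patients per hospital-period. A reader judging feasibility would think that four in five hospitals comfortably exceed the planning rate, when more than half recorded 10 patients or fewer.
- **The denominator.** The sample size is given as patients or participants, while the primary outcome is measured only in those with a primary anastomosis. The single stated inflation is for unequal recruitment. If the 4,440 includes patients without an anastomosis, fewer than 4,440 contribute to the primary outcome. The loss cannot be assumed to be nil: ileostomy without anastomosis is a secondary outcome, and the checklist explicitly asks for a decision between anastomosis and a stoma alone.
- **The effect label.** A reduction from 8.1% to 5.6% is called a 30% relative reduction, which is slightly less than those rates imply.

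At stake are an accurate feasibility statement and a stated power whose conditions the reader can see.

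**Working it through.** **1. Share of sites above 10 patients (Table 1).**

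Total: 53 + 104 + 63 + 39 + 17 + 8 = 284, matching the stated number of centres.

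- Above 10: 63 + 39 + 17 + 8 = 127; 127/284 = 44.7%.
- Above 5: 284 − 53 = 231; 231/284 = 81.3%.
- 10 or fewer: 53 + 104 = 157; 157/284 = 55.3%.

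The printed percentages agree with the counts, so the table is internally sound. The 81% belongs to the threshold of 5.

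**2. Does this move the sample size?** The required input is a mean of 10. The audit mean is 3,208/284 = 11.3, taken from totals and not from the 81%. No sample-size figure changes.

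**3. Reproducing the stated size.** Inputs: p1 = 0.081, p2 = 0.056, 80% power, 5% significance (taken as two-sided), ICC ρ = 0.05 without decay, m = 10 per hospital-period.

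*Individually randomised size, pooled formula without continuity correction, p̄ = 0.0685:*

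n per arm = [1.96 √(2p̄(1−p̄)) + 0.842 √(p1(1−p1) + p2(1−p2))]² / (p1−p2)² = 1,602, so 3,204 in total.

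*Dog-leg design effect.* Three sequences give four hospital-periods per three hospitals, because only the middle sequence is measured twice. With a fixed period effect, the treatment estimate averages the two within-period contrasts, and

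DE = 1 + (m−1)ρ − mρ/2 = 1 + 0.45 − 0.25 = 1.20.

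*Result:* 3,204 × 1.20 = 3,845 patients; 3,845 / (10 × 4/3) = 288 clusters. The protocol states 3,895 and 292, about 1.3% higher. Then 3,895 × 1.14 = 4,440 and 292 × 1.14 = 333. The stated size is reproduced.

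**4. Power at 333 clusters.** Treat the 14% as fully used: 333/1.14 = 292.1 effective clusters. At m = 10 that is 3,895 patients, and 3,895/1.20 = 3,246 on the individually randomised scale. With n = 3,246/2 = 1,623 per arm,

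power = Φ{[0.025√n − 1.96√(2p̄(1−p̄))] / √(p1(1−p1) + p2(1−p2))} = 80.5%.

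**5. Some enrolled patients without an anastomosis.** The protocol gives no proportion, so the shares below are assumptions. If a share q has none, the analysable number per period is m = 10(1−q), and DE = 0.95 + 0.025m.

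| Assumed share without anastomosis | Analysable of 4,440 | Power, 8.1% vs 5.6% |
|---|---|---|
| 0% | 4,440 | 80.5% |
| 2% | 4,351 | 79.9% |
| 5% | 4,218 | 78.9% |
| 10% | 3,996 | 77.1% |

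**6. The effect label.** 1 − 5.6/8.1 = 30.9%, whereas 0.70 × 8.1% = 5.67%. At 5.67%, power with all 4,440 anastomosed is 78.1%. Reaching 80% there would take 1,704 per arm: 3,408 × 1.20 × 1.14 = 4,662 patients, or about 350 clusters.

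**The case against.** A reader might infer that the planning figures fail and that 80% power is not delivered. The case against that reading is strong.

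- The 81% sentence does not carry the calculation. The mean of 10 does, and 11.3 supports it. A mean of 11.3 is compatible with 45% of sites above 10. This stands.
- The protocol never says that its 4,440 counts every eligible right colectomy. A calculation on leak rate may already have meant patients at risk of a leak. This stands as far as it goes: the text is ambiguous, not demonstrably wrong.
- Nothing makes 4,440 a stopping target. The Study Design section plans in hospitals (7 phases of 48, or 336, against 333 required), and the analysis takes all patients recorded in the scheduled periods. There is also a sample-size review after 50 centres complete baseline recruitment, though no anastomosis fraction is mentioned there.
- At the audit rate of 11.3 per period, the same calculation gives 82.6% power with 5% lacking an anastomosis and 81.0% with 10%. About 11% could lack one and still leave 11.3 × 0.89 ≈ 10 analysable per period. Two limits apply. This means about 333 × 4/3 × 11.3 ≈ 5,017 enrolled, not 4,440. The protocol also does not say whether all 3,208 audit cases had an anastomosis.
- The 14% is described as an upper bound, so treating it as fully used makes the powers above conservative.
- The 30% label is rounding, since both absolute rates are stated with it and the calculation uses them.

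What survives is the contradiction with Table 1, the undefined counting unit, and a small labelling inaccuracy.

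**Conclusion.** The 81% figure is an error on the protocol's own data: 45% of audit sites exceeded 10 patients. It misstates the feasibility evidence and leaves the sample size unchanged.

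The counting unit is a real gap with a modest consequence. The 80% power is correct for 8.1% versus 5.6% if all 4,440 patients have a primary anastomosis, and there is only about half a point of slack. If the 4,440 and the 10 per period include patients without one, power slips below 80% from about 2% of patients and is roughly 1 to 3 points below nominal at 5% to 10%. Those shares are assumptions, and recruitment at the audit mean would absorb them. The documents therefore support saying that 80% power is conditional on an unstated assumption. They do not support saying that the trial is underpowered.

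The 30% label costs about 2 points if read literally (78.1% at 5.67%). It should not be added to an unsourced anastomosis share to produce a headline shortfall.

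**What to change.** 1. In Projected Recruitment, change the sentence to say that 45% of sites recruited more than 10 patients (81% more than 5).
2. In Sample Size and the summary, state that 10 per hospital-period and 4,440 count patients with a primary anastomosis. Alternatively, keep 4,440 as enrolled patients and restate the power under a declared proportion without an anastomosis.
3. Describe the target effect as 8.1% to 5.6%, about 31% relative, and note that power at exactly 30% (5.67%) is about 78%.

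The cost is a text correction and possibly a slightly lower stated power. No extra patients are needed for the correction. If the first option in item 2 is chosen, the enrolled number will exceed 4,440 by the share without an anastomosis. At an assumed 5% that is 10/0.95 = 10.5 enrolled per period, within the audit mean of 11.3 and with no added hospitals.
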